## SCHEMA

Patient Population: (see section 3.0 for complete eligibility criteria)

- Age  $\geq 70$  and/or Charlson Comorbidity Score  $\geq 2$
- Biopsy proven prostate adenocarcinoma
- No clinical or radiographic evidence of metastatic disease
- By risk groupings, 2+ intermediate risk factors or 1+ high risk factor
- Zubrod performance status  $\leq 2$
- No history of androgen deprivation therapy (ADT) [GnRH agonist or antiandrogen]
- No prior pelvic radiation

Required Sample Size: Minimum of 40 experimental subjects and 30 control subjects (total of 70).

Study Center:

University of Chicago Medical Center,.

Concept and Rationale: Randomized data support the addition of ADT to standard dose external beam radiation (RT) in men with non-metastatic, intermediate and high risk prostate cancer. However, the role of medical castration with ADT is less certain when dose-escalated RT is administered. In particular, the benefit of standard ADT remains unclear in older men and in those with medical comorbidities in whom the risks of therapy may be heightened. Therefore, we propose to de-intensify standard ADT in this population, in favor of dual oral androgen manipulation with an antiandrogen and a 5-alpha reductase inhibitor (5AR). We hypothesize that health-related quality of life (HRQOL) will be improved with the removal of the gonadotropin releasing hormone (GnRH) and that oncologic outcomes will not be compromised. Dual oral androgen manipulation therapy will be delivered prior to and concurrent with dose-escalated radiation with the goal of maximizing its anti-tumoral effect.

Primary Objective: To test the hypothesis that health-related quality of life (HRQOL) of men over 70 and/or with medical comorbidities treated with oral androgen manipulation and radiation (RT) will be improved compared to that of patients undergoing standard ADT and RT.

Secondary Objectives: To test the hypothesis that the oncologic outcomes of patients treated with dual oral androgen manipulation with RT will be comparable to the outcomes of patients undergoing standard ADT with RT.

Study Design: Single arm prospective, feasibility trial. A synchronous control cohort receiving standard ADT will be followed for collection of data on HRQOL endpoints.

Statistical Methods:

Patient reported data will be grouped into summary scores in each relevant quality of life domain (sexual, urinary, bowel, hormonal/vitality). Quality of life and toxicity scores will be compared to those of patients in the synchronous control cohort receiving standard ADT with radiation. Univariate analysis of mean scores will be performed using a two sample t-test. Scores will also be compared between trial patients and the control cohort while controlling for covariates using linear regression analysis.

## **1. OBJECTIVES**

### **1.1. Primary Objectives**

The broad objective is to test the feasibility of delivering dual oral androgen manipulation with an antiandrogen and a 5-alpha reductase (5AR) inhibitor in conjunction with dose-escalated radiation (RT) in intermediate and high risk prostate cancer patients 70 years of age or older and/or with moderate to severe medical comorbidities. The primary objective is to test the hypothesis that health-related quality of life (HRQOL) in patients treated with dual oral androgen manipulation will be improved compared to that of controls treated with standard androgen deprivation therapy (ADT) including a gonadotropin releasing hormone (GnRH) agonist +/- an antiandrogen.

### **1.2. Secondary Objectives**

The secondary objective is to test the hypothesis that oncologic outcomes including biochemical progression free survival, distant metastasis free survival, cause specific survival, and overall survival after treatment with dual oral androgen manipulation and dose escalated radiation will be comparable to the outcomes of patients treated with standard ADT.

### **1.3. Tertiary Objectives**

For select men who consent to a research biopsy, we would like to analyze the RNA expression of prostate cancers treated with hormonal therapy prior to radiation for prostate cancer. We would a comparison using tissue from the same patient, before any treatment (initial biopsy) and then after two months of ADT (at the time of fiducial marker placement) to show how RNA expression changes in the tumor of the prostate with ADT. We would also compare differences in expression across the 2 cohorts of patients, treated with oral-only ADT and traditional injectable ADT. The hypothesis is that oral-only ADT would induce similar changes within the tumor, thus complementing the clinical outcome evaluation (primary and secondary objectives) with a mechanistic evaluation.

## **2. BACKGROUND**

### **2.1. Intermediate and High Risk Prostate Adenocarcinoma**

Prostate cancer is the most common non-dermatologic malignancy and the second leading cause of cancer-related death in men in the United States. In 2010, an estimated 217,730 men will be diagnosed with prostate cancer, and 32,050 will die of their disease.[1] Prostate cancer is predominately a disease affecting older men, with 75% of cases diagnosed in men aged 65 and older.[2] Despite a trend toward earlier stage at diagnosis with the widespread use of prostate specific antigen (PSA) screening, a significant percentage of patients are diagnosed with advanced disease. In an analysis of over 10,800 men with prostate cancer diagnosed between 1990 and 2007, over 50% of patients entering the cohort between 2004 and 2007 were diagnosed with intermediate or high risk prostate cancer. [3]

Multiple treatment options exists for intermediate and high risk prostate cancer ranging from active surveillance to aggressive combined modality therapy with surgery and/or radiation with or without androgen deprivation therapy (ADT). Treatment decisions involve consideration of disease features including clinical T stage, PSA, and Gleason score. In addition, the therapeutic approach should take into account comorbidities, quality of life concerns, and patient preferences.

Therapeutic decision-making can be particularly complicated in men with a limited life expectancy. In these cases, weighing the oncologic benefits of treatment against the possibility of toxicity related to a given therapy is clouded by competing risks of mortality related to comorbid illnesses and aging. The majority of patients with intermediate or high risk disease will undergo definitive therapy including either surgery or radiation, but advanced age and comorbidities are known to influence the choice of primary treatment. In one series of over 11,000 patients, 4% of those over age 75 underwent surgery as primary therapy compared to 60% of patients under the age of 75. [4] Patients who are elderly or who have multiple medical illnesses are more likely to receive external beam radiation than younger, healthier men.[5]

## 2.2. Rationale

Extensive evidence from randomized trials demonstrates a benefit in PSA control, cause-specific, and in some cases, overall survival, with the addition of ADT to radiation in men with both intermediate [6, 7] and high risk prostate cancer [8-10]. In these randomized trials, radiation was delivered to doses on the order of 66-70 Gy. With improvements in techniques for radiation delivery, doses can now be safely escalated upwards of 80 Gy with significant improvements in disease control. Multiple randomized trials have demonstrated absolute improvements in 5-year biochemical control in all risk groups by 10 to 20% with doses in the range of 74-80 Gy.[11-15] Dose escalated radiation has therefore become standard practice in patients receiving radiation alone; however, the role of dose escalated radiation in combination with ADT in patients with intermediate and high risk disease has not been fully elucidated. This is, in large part, the rationale for the ongoing Radiation Therapy Oncology Group 0815 trial which randomizes patients with intermediate risk prostate cancer to 79.2 Gy of radiation with or without Leuprolide and Bicalutamide.

While the benefits of ADT have been well-established in randomized trials, so have the toxicities; androgen blockade with a GnRH agonist has well-known potential adverse effects including sexual dysfunction (loss of libido, impotence), decreased bone mineral density, hot flashes, hematologic toxicity (anemia), fatigue, hyperglycemia, hypercholesterolemia, hypertension, anxiety, depression, breast tenderness, and pain. For complete androgen blockage, GnRH agonists are commonly given in conjunction with a nonsteroidal antiandrogen (e.g. bicalutamide). However, the side effects of ADT are, for the most part, driven by the GnRH agonist component of treatment, which induces a castrate state. In a randomized comparison of bicalutamide monotherapy versus leuprolide monotherapy for nonmetastatic prostate cancer, bicalutamide monotherapy increased bone mineral density and resulted in less fatigue, sexual dysfunction, fat accumulation, and vasomotor flushing than leuprolide monotherapy. [16]

Due to the significant toxicities associated with ADT, and the uncertain benefit in the setting of dose escalation, the role of ADT in the elderly and in patients with significant comorbidities is particularly unclear. Some question the role of further testosterone suppression in elderly men in whom up to 80% meet the criteria for hypogonadism before treatment.[17] Furthermore, the elderly may have heightened sensitivity to the adverse effects of ADT resulting in more severe quality of life detriment than in younger patients. In a randomized trial from Harvard showing an overall survival benefit with the addition of short-term ADT to radiation in intermediate and high risk patients, a post-randomization analysis revealed a significant interaction between

comorbidity score and the effect of ADT on survival. In patients with moderate or severe comorbidities, the survival benefit to adding ADT to radiation was lost. [18] The lack of benefit to ADT seen in some groups may in part be due to hastening of cardiovascular disease, and thus death due to causes other than prostate cancer. Furthermore, given the long natural history of prostate cancer, the beneficial effects of ADT may be masked by competing causes of mortality in aging and unhealthy populations who are unlikely to benefit from aggressive therapy.

However, there is some clinical evidence in support of the use of ADT even in the elderly or those with significant comorbidities. A reanalysis of the Radiation Therapy Oncology Group (RTOG) 85-31 trial comparing ADT until progression versus no ADT in patients treated with radiation for high risk non-bulky disease, there was no impact of hormonal therapy on the risk of cardiovascular mortality.[19] In the Harvard randomized study of radiation with or without short term ADT, of 206 patients enrolled, there were 78 with mild or no comorbidity who were over the age of 72. Among the 70% of these men who were healthy, all cause mortality at 8 years was 16% in those treated with ADT plus radiation compared to 41% in those receiving radiation alone.[20] More investigation is warranted to clarify the risks and benefits of ADT in addition to radiation in patients with medical comorbidities and advanced age in order to improve patient selection.

One alternative to medical castration with a GnRH agonist is nonsteroidal antiandrogen monotherapy. Due to the aforementioned toxicity profiles, bicalutamide monotherapy has been studied in the setting of locally advanced, node positive, recurrent, and metastatic prostate cancer as an alternative to gonadal suppression. A multicenter randomized trial comparing bicalutamide monotherapy to medical or surgical castration in patients with locally advanced or metastatic disease revealed no difference in disease progression or overall survival with a median 6.5 years follow-up in the group without metastases. In addition, measures of sexual interest, physical capacity, and bone mineral density were significantly higher in the bicalutamide arm.[21] In contrast, gynecomastia and breast pain were more common in the group treated with bicalutamide alone.

The Bicalutamide Early Prostate Cancer Program is the largest study of bicalutamide monotherapy as an adjuvant to standard treatment in patients with localized or locally advanced prostate cancer. The study was comprised of 3 parallel trials: one in North America (trial 23), one in Mexico, South Africa, Australia, and Europe (trial 24), and one in Scandinavia (trial 25). The trials randomized over 8,000 patients to placebo or bicalutamide (150 mg QD) following the standard therapy of choice including watchful waiting (in trials 24 and 25 only), radical prostatectomy, or radiation. In 1,370 patients who underwent radiation (median dose 64 Gy) with a median follow-up of over 7 years, patients randomized to bicalutamide after radiation had prolonged biochemical and objective progression free survival compared to those receiving placebo (HR 0.61 and HR 0.75, respectively). Furthermore, patients treated with bicalutamide with locally advanced disease (T3-T4 or N1 M0) had superior overall survival to those receiving placebo (HR 0.65).[22] This overall survival benefit is in line with the 23% reduction in overall deaths seen in RTOG 85-31 which randomized patients with locally advanced, non-bulky disease to radiation followed by goserelin or radiation alone.[23]

Another class of testosterone modulators, 5-alpha reductase (5AR) inhibitors, blocks the intraprostatic conversion of testosterone to its more potent form, dihydrotestosterone. In addition, 5AR inhibitors down-regulate androgen receptor expression and may decrease the rate of subsequent androgen independent prostate cancers. [24] Dutasteride and finasteride are

effective in the treatment of benign prostatic hyperplasia and male pattern baldness, and they are generally well tolerated because serum testosterone levels are maintained. The Prostate Cancer Prevention Trial (PCPT) compared finasteride to placebo in men at high risk for prostate cancer; men randomized to finasteride had a 25% reduction in the incidence of prostate cancer.[25] A similar effect was noted in a randomized study testing dutasteride to placebo for the prevention of prostate cancer in men at high risk; the relative risk reduction with the use of dutasteride was 23% for the incidence of prostate cancer over 4-years.[26] As monotherapy for either localized or advanced prostate cancer, 5AR inhibitors may have some effect on progression of disease, however no studies have confirmed an effect on survival. [27-29]

Several phase II trials have investigated 5AR inhibitors in combination with antiandrogens with promising findings. A CALGB study investigated the role of finasteride plus flutamide in 101 patients with rising PSA after definitive surgery or radiation therapy. In 98.6% of patients, PSA was reduced 80% below baseline. Approximately 2/3 of patients achieved undetectable PSA levels, and amongst this group, only one patient progressed with a median of 16 months follow up. [30] In sequential phase II studies at Walter Reed Army Medical Center, patients with rising PSA after definitive treatment received either combined flutamide and finasteride or flutamide monotherapy. In comparing the two cohorts, those receiving combined therapy had greater PSA decreases and lower nadir values. On multivariable analysis, patients on combined therapy were less likely to progress (HR 0.21). There was no difference in the frequency of side effects between the two arms. [31] In the setting of metastatic prostate cancer, a UK randomized trial compared goserelin plus flutamide versus goserelin plus finasteride versus flutamide plus finasteride. The PSA value at 24 weeks decreased 97-99% from baseline and was no different between the 3 groups, although the group that was spared from goserelin therapy appreciated less sexual toxicity. [32]

Dual oral androgen manipulation has not been formally investigated as definitive treatment for untreated prostate cancer, nor as a concurrent therapy with radiation. The proposed study will investigate the role of dual oral androgen manipulation overlapping with radiation as an alternative to a GnRH agonist. We hypothesize that the proposed treatment will result in less quality of life decline than standard therapy. In this study, we aim to demonstrate the feasibility of administering radiation therapy with oral hormonal therapy to a population of prostate cancer patients of advanced age or with comorbidities and to demonstrate the feasibility of evaluating a number of quality of life endpoints. After some preliminary data are established, we anticipate moving forward with a larger phase II study design, testing radiation therapy with oral only versus standard hormonal therapy, with a primary endpoint of quality of life. Disease outcome would be an important secondary endpoint; we also theorize that dual oral androgen manipulation will impart some anti-tumoral effect or radiosensitization, thus resulting in acceptable oncologic outcomes. The data from this larger randomized phase II study could then potentially contribute towards a phase III, cooperative group, randomized study testing for a quality of life benefit, or for non-inferiority regarding efficacy of therapy.

### **3. PATIENT SELECTION**

#### **3.1. Eligibility Criteria**

3.1.1. Age  $\geq$  70 years

AND/OR

Charlson comorbidity index score  $\geq$  2 (see Appendix C)

(Prostate cancer diagnosis does not contribute to total score)

3.1.2. Pathologically (histologically) proven diagnosis of prostatic adenocarcinoma.

3.1.3. Intermediate or high risk for recurrence according to the following criteria:

Two or more of the following intermediate risk features for recurrence

- Gleason Score = 7
- PSA 10-20 ng/ml
- Clinical Stage T2b-T2c
- Percent positive biopsy cores  $\geq 50\%$

**OR**

One or more of the following high risk features for recurrence

- Gleason Score 8-10
- PSA >20 ng/ml
- Clinical Stage T3a-T4

3.1.4. Clinically negative lymph nodes as established by imaging (pelvic +/- abdominal CT or MRI), nodal sampling, or dissection, except as noted immediately below:

- Patients with intermediate risk factors only do not require abdominopelvic imaging, but these studies may be obtained at the discretion of the treating physician.
- For men with any high risk feature (psa > 20, gleason score >8, or clinical stage T3), a pelvic CT or MRI, are required. It is recommended that the duration between these scans and study registration be less than 60 days, but if the time period is >60 days and the opinion of the clinician is that repeat studies would offer limited benefit, then these studies do not need to be repeated. A lymph node will be considered radiographically positive if it is >1.5cm in size, occurs within the expected distribution for prostate cancer metastasis (i.e. internal iliac or obturator fossa), and is without classic benign features (i.e. fatty hilum). Patients with lymph nodes equivocal or questionable by imaging are eligible for inclusion in this study.

3.1.5. No evidence of bone metastases (M0) on bone scan.

- Patients with intermediate risk factors only do not require a bone scan, but these studies may be obtained at the discretion of the treating physician.
- Patients with any high risk factors are required to undergo a bone scan. It is recommended that the duration between these scans and study registration be less than 60 days, but if the time period is >60 days and the opinion of the clinician is that repeat studies would offer limited benefit, then these studies do not need to be repeated.
- Equivocal bone scan findings are allowed if additional imaging (e.g. plain film x-rays, or CT) does not confirm metastasis.

3.1.6. History/physical examination (to include, at a minimum, digital rectal examination of the prostate and examination of the skeletal system and abdomen, and formal comorbidity assessment via the Charlson Comorbidity Index within 60 days prior to registration.

3.1.7. Zubrod Performance Status 0-2

- 3.1.8. Age  $\geq$  18
- 3.1.9. Baseline serum PSA value performed with an FDA-approved assay (e.g., Abbott, Hybritech) within 60 days prior to registration
- 3.1.10. Baseline serum testosterone obtained within 60 days prior to registration
- 3.1.11. Study entry PSA and serum testosterone must not be obtained during the following time frames: (1) 10-day period following prostate biopsy; (2) following initiation of oral androgen manipulation; (3) within 30 days after discontinuation of finasteride or dutasteride
- 3.1.12. CBC/differential obtained within 60 days prior to registration with adequate bone marrow function defined as follows:
- Absolute neutrophil count (ANC)  $\geq$  1,800 cells/mm^3
  - Platelets  $\geq$  100,000 cells/mm^3
  - Hemoglobin  $\geq$  8.0 g/dl (Note: The use of transfusion or other intervention to achieve Hgb  $\geq$  8.0 g/dl is acceptable.)
- 3.1.13. Patient must be able to provide study-specific informed consent prior to study entry.
- 3.1.14. Liver function parameters as follows:
- Total Bilirubin  $\leq$  2 x institutional upper limit of normal
  - AST (SGOT) or ALT (SGPT)  $\leq$  2 x institutional upper limit normal

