## **3.2. Exclusion Criteria**

- 3.2.1. Prior radical surgery (prostatectomy), high-intensity focused ultrasound (HIFU) or cryosurgery for prostate cancer
- 3.2.2. Prior hormonal therapy, such as LHRH agonists (e.g., goserelin, leuprolide), antiandrogens (e.g., flutamide, bicalutamide), estrogens (e.g., DES), or bilateral orchiectomy
- 3.2.3. Use of 5-alpha reductase inhibitors (finasteride, dutasteride) specifically prescribed for the treatment of prostate cancer.
- 3.2.4. Prior or concurrent cytotoxic chemotherapy for prostate cancer; prior chemotherapy for a different cancer is permitted.
- 3.2.5. Prior radiation, including brachytherapy, to the region of the prostate that would result in overlap of RT fields.
- 3.2.6. Active lupus or scleroderma

3.2.7. Severe, active co-morbidity, including but not limited to:

- 3.2.7.1. Unstable angina within the last 6 months without subsequent corrective cardiovascular procedure.
- 3.2.7.2. Acute bacterial or fungal infection requiring intravenous antibiotics at the time of registration.
- 3.2.7.3. Hepatic insufficiency with AST, ALT, or Bilirubin > 2 x upper limit of normal, clinical jaundice, and/or coagulation defects
- 3.2.7.4. Acquired Immune Deficiency Syndrome (AIDS) based upon current CDC definition; note, however, that HIV testing is not required for entry into this protocol. Patients who are HIV seropositive but do not meet criteria for diagnosis of AIDS are eligible for study participation.

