## **4. TREATMENT PLAN**

### **4.1. Dual Oral Androgen Manipulation**

Treatment will be administered on an outpatient basis. Reported adverse events and potential risks are described in Section 6.

After study enrollment, patients will initiate dual oral androgen manipulation therapy consisting of an androgen receptor blocker and a 5AR inhibitor according to the following dose and route schedules:

- Bicalutamide 50 mg PO daily
- Dutasteride 0.5 mg PO daily (recommended) or Finasteride 5 mg PO daily

During week 6-8 of oral androgen manipulation therapy, patients will undergo CT simulation for radiation planning. After 8 weeks of hormonal therapy, patients will begin dose escalated radiation with concurrent androgen manipulation for approximately 7-8 weeks, Monday through Friday. Details regarding planning and administration of RT are described in Section 5.

Following completion of radiation, having completed 4 total months of dual androgen manipulation, patients will discontinue Bicalutamide. All patients will continue taking the 5AR inhibitor as monotherapy for 2 years after completion of radiation for a total of 2 years, 4 months of treatment.

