#### 4.9 Tissue Collection

For patients consenting to tissue collection portion of the study, the first block of FFPE tissue will be taken from the left over samples of Prostate biopsy done at initial diagnosis. If the patient has more than one diagnostic biopsy then tissue will be taken from the most recent biopsy sample.

A research biopsy will be collected at the time of intra-prostatic fiducial marker placement, after the initial 2 months of hormonal therapy. The marker placement is considered standard of care therapy, using a transrectal ultrasound probe (similar to the approach for a prostate biopsy). The biopsy would include patients in both treatment and control group. If the patient has had prior MRI, these images can be fused to the ultrasound using software (UroNav) which will increase the yield of the biopsy for tumor. The tissue collected will be stored at HRTC.

The following tables outline the requirements for tissue banking. Tissue will be collected and stored for batched future analysis.

Biospecimen Type	Collection time point	Number of samples
------------------	-----------------------	-------------------

A paraffin embedded tissue block of primary prostate cancer taken at initial diagnostic biopsy (left over sample)	Pretreatment, before starting any hormonal therapy	1 block
2 cores of paraffin embedded tissue of tumor	After 2 months of hormonal therapy at the time of fiducial marker placement , for consenting patients	2 blocks of FFPE

Tumor biopsy for molecular analysis will be conducted. Either fresh tissue or archived paraffin embedded specimens will be used for analysis. RNA from tumor samples will be isolated using standard techniques. We would like to 1) analyze intra-patient differences in RNA expression at initial biopsy specimen and after two months of hormonal therapy, and 2) compare the inter-patient differences in RNA expression in the oral ADT cohort versus the traditional injectable ADT cohort to test the hypothesis that oral-only ADT results in a similar RNA expression profile to traditional therapy.

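### Section 3.1.11 bars an entry PSA for 30 days after a 5AR inhibitor is stopped but not while it is taken, so an on-drug PSA can set risk group and imaging requirements

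*Combined protocol and SAP*

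**What the plan says.** Section 3.1.11 lists three periods in which entry PSA and testosterone may not be obtained: the 10 days after a prostate biopsy; the time "following initiation of oral androgen manipulation"; and "within 30 days after discontinuation of finasteride or dutasteride". Current use of a 5AR inhibitor is not among them.

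Section 3.2.3 excludes "Use of 5-alpha reductase inhibitors (finasteride, dutasteride) specifically prescribed for the treatment of prostate cancer". The separate exclusion for earlier hormone treatment, 3.2.2, reads "Prior hormonal therapy, such as LHRH agonists (e.g., goserelin, leuprolide), antiandrogens (e.g., flutamide, bicalutamide), estrogens (e.g., DES), or bilateral orchiectomy" and does not name these drugs. The Schema's item on previous ADT names only GnRH agonists and antiandrogens. Section 2.2 notes that dutasteride and finasteride are used for benign prostatic hyperplasia and baldness.

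PSA enters eligibility twice. In 3.1.3 a value of 10-20 ng/ml is one intermediate risk feature, of which two are needed, and a value above 20 is by itself a high risk feature. A high risk feature makes pelvic CT or MRI (3.1.4) and a bone scan (3.1.5) compulsory. By contrast, "Patients with intermediate risk factors only do not require abdominopelvic imaging", and the same holds for the bone scan. In both cases the treating physician may still order the study.

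**The concern.** The rule gives the reverse of what its own logic suggests. A PSA drawn two weeks after the last tablet is refused, while one drawn on a day the man took the tablet is not. Clause (3) has a purpose only if these drugs are thought to disturb the entry laboratory values, so a value taken during use should be at least as suspect.

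Two errors could follow. A man whose only high risk feature is a PSA above 20 could read at or below 20 and be classed as intermediate risk, where staging imaging is optional rather than required. Or a man could read below 10, lose his PSA feature and, if he has too few others, be screened out. Section 4.3 draws controls from men who meet the same eligibility criteria, so the gap exists in both cohorts.

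**Working it through.** There is no plan figure to reproduce, because this is an eligibility rule. The check has a textual part and an illustration.

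**Text**

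1. Can a current user enter? Section 3.2.3 turns on the reason for prescribing. A man on finasteride or dutasteride for benign disease is not caught by it, nor by the examples in 3.2.2, nor by the Schema. He is eligible.
2. Does clause (2) of 3.1.11 cover him? It uses the protocol's name for study treatment. Section 4.1 says that after enrolment "patients will initiate dual oral androgen manipulation therapy consisting of an androgen receptor blocker and a 5AR inhibitor". A 5AR inhibitor taken alone, earlier, for another purpose does not plainly fit.
3. Does clause (3) cover him? It starts when the drug is stopped. It does not.
4. Is there a correction elsewhere? Section 3.1.9 asks for an FDA-approved assay within 60 days before registration and says nothing about 5AR inhibitors. No section adjusts the PSA.

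**Direction of effect.** Section 2.2 reports larger PSA falls and lower nadirs with flutamide plus finasteride than with flutamide alone, in sequential phase II cohorts. Section 6.1.1 lists a rise in serum testosterone among the effects of dutasteride. Neither gives the size of the PSA change from a 5AR inhibitor alone.

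**Illustration.** Let f be the on-drug PSA as a fraction of the off-drug PSA. The range f = 0.4 to 0.7 is an assumption. Off-drug PSA = reading / f.

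| f | Reading of 20 stands for | Reading of 10 stands for | Off-drug 20.1 reads |
|---|---|---|---|
| 0.7 | 20/0.7 = 28.6 | 10/0.7 = 14.3 | 20.1 × 0.7 = 14.1 |
| 0.5 | 20/0.5 = 40.0 | 10/0.5 = 20.0 | 20.1 × 0.5 = 10.1 |
| 0.4 | 20/0.4 = 50.0 | 10/0.4 = 25.0 | 20.1 × 0.4 = 8.0 |

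So off-drug values from just above 20 up to 29-50 ng/ml would not register as high risk. Values from 10 up to 14-25 would read below 10 and lose the PSA feature.

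**Who is affected.** A man must be a current user for benign disease, his off-drug PSA must lie in one of those bands, and PSA must decide his classification. A man with Gleason 8-10 or stage T3a-T4 is high risk whatever his PSA reads. To enter as intermediate risk, a man must also have enough other features: one more if the reading is 10-20, two if it is below 10.

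**The case against.** The strongest reply is that this is a drafting slip and not a policy. A ban for 30 days after stopping makes sense only if on-drug values are unusable too, and a sensible site might stretch clause (2) to say so. Section 3.1.3 also does not state that the 3.1.9 baseline draw must be the PSA used for classification, so a site could use the diagnostic value. Both points are fair. They show that the text permits the error, not that it requires it. They do not remove the need for the correction, because the written rule leaves the choice to each reader.

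Three stronger conclusions might be drawn, and the documents do not support them.

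- *Men with undetected nodal or bone disease will be enrolled.* This needs an on-drug reading that hides a decisive PSA, a physician who does not use the discretion that 3.1.4 and 3.1.5 leave open, and disease actually present. Nothing in the documents measures that chain.
- *Two to eight of the 40 experimental men are affected.* That is 5% and 20% of 40 (0.05 × 40 = 2; 0.20 × 40 = 8) under an assumed rate of drug use. It would count users, not men whose classification changes, and the documents give no rate.
- *One user would distort the RNA comparison in the tissue subset.* Section 3.1.11 does not govern tissue. Section 4.9 already asks that the first block be "Pretreatment, before starting any hormonal therapy", and 4.1 uses the term hormonal therapy for a regimen that includes a 5AR inhibitor. No calculation supports a distortion.

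**Conclusion.** The point holds as a gap in a stated rule. Sections 3.1.11 and 3.2.3 together let an on-drug PSA stand as the entry value while a PSA taken up to 30 days after stopping is refused. The wording gap is certain. Its effect is not: the number of men is unknown and probably small, and the PSA bands rest wholly on the assumed 40-70%.

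The consequence is confined to risk grouping, eligibility, whether staging imaging is compulsory, and the meaning of the baseline PSA and testosterone. The primary endpoint in 9.1 is HRQOL at 6 months and does not use PSA, so neither it nor the sample size in 9.2 is affected. For PSA failure, 9.3 already disclaims formal conclusions. The correction is worth making because it is cheap and the rule decides who enters and who must be imaged.

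**What to change.** Reconcile 3.1.11 with 3.2.3, 3.1.9 and 3.1.10:

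1. Extend clause (3) to the time on finasteride or dutasteride as well as the 30 days after stopping, for the purposes of risk classification and the imaging triggers.
2. State that, for a current user, a documented PSA from before the drug was started governs 3.1.3-3.1.5. The sponsor should set a limit on its age and say in advance how a man with no usable earlier value is handled.
3. Add an explicit exception so that the 60-day baseline PSA and testosterone may still be drawn during use and flagged as on-drug. Without it, a bare ban during use would leave a current user unable to satisfy 3.1.9 and 3.1.10, and so ineligible unless he stopped the drug.
4. Flag 5AR inhibitor use in both cohorts. The study calendar (Section 7) already documents medicines at baseline for trial patients, and 4.3 allows the medical record to be used for controls, so no new visit or test is needed.

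The cost is a short amendment, one derived flag and a chart look-up for a few men, some of whom may have no suitable earlier PSA. Study treatment does not change.
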